5.5 Justification for Dose

Please refer to individual FRACTION-RCC Sub-Protocols for their respective dose justifications.

6 STUDY POPULATION

For entry into the FRACTION-RCC study (per FRACTION-RCC Master Protocol), the following criteria MUST be met prior to dosing on Day 1. For entry into a study treatment per a FRACTION-RCC Sub-Protocol, additional treatment-specific criteria, if applicable, must also be met.

No exceptions will be granted.

6.1 Inclusion Criteria

1) Signed Written Informed Consent

- a) Participants must be able to give self-consent and then sign and date an IRB/Independent Ethics Committee (IEC)-approved written informed consent in accordance with regulatory and institutional guidelines. This must be obtained before the performance of any protocol-related procedures that are not considered part of normal patient care.
- b) Participants must be willing and able to comply with scheduled visits, treatment schedule, laboratory testing, and other requirements of the study.
- c) Participants must provide consent for 3 mandatory tumor biopsy samples (as detailed in “2)j)” below).

2) Type of Participant and Target Disease Characteristics

- a) All participants must have advanced (not amenable to curative surgery or radiation treatment) or metastatic (American Joint Committee on Cancer Stage IV) RCC
- b) Histological confirmation of RCC with a clear-cell component
- c) Prior adjuvant or neoadjuvant treatment with IL-2, INF α , or radiotherapy is permitted as long as the last administration of the last regimen (whichever was given last) occurred at least 4 weeks prior to randomization.
- d) Prior treatment with targeted agents such as TKIs or antiangiogenic monoclonal antibodies are eligible.
- e) Track-specific eligibility criteria
 - i) Track 1: anti-PD-1, anti-PD-L1, or anti-CTLA-4 treatment-naïve participants
 - (1) Participants must not have received any anti-PD-1, anti-PD-L1, or anti-CTLA-4 treatment, prior to this study. Participants previously treated with agents other than anti-PD-1, anti-PD-L1, or anti-CTLA-4 are eligible for Track 1.
 - (2) Participants may have had prior treatment for progressive or recurrent disease.
 - (a) Participants who have received IL-2 or INF α are eligible.
 - (b) Participants may have received targeted treatment (see above)
 - (3) Not applicable per Amendment 02.
 - (4) After signing informed consent, participants will be required to submit a fresh tumor biopsy prior to treatment as described below [see “6.1.2)j)”]. Participants must have an adequate tumor biopsy (as determined by a central laboratory pathologist or a local pathologist) prior to randomization.
 - (5) Participants must be evaluated for risk of the disease as defined by International Metastatic RCC Database Consortium (IMDC) score. ([Appendix 8](#)).
 - (6) Based on the results from CheckMate-214⁵³, participants with favorable risk profile by IMDC Score must have been treated with sunitinib prior to randomization into Track 1 nivolumab plus ipilimumab.
 - (7) Karnofsky Performance Status (KPS) must be $\geq 70\%$ ([Appendix 7](#)).

- ii) Track 2: anti-PD-1, anti-PD-L1, or anti-CTLA-4 treatment-experienced participants
 - (1) Participants must have had progressive or recurrent disease during or after anti-PD-1, anti-PD-L1, or anti-CTLA-4 treatment. (Participants treated with any study treatment targeting PD-1, PD-L1, or CTLA-4 will be considered anti-PD-1, anti-PD-L1, or anti-CTLA-4 treatment experienced, respectively.)
 - (2) Participants who have had prior treatment with any of the agents (or any other agent targeting PD-1, PD-L1, or CTLA-4) in monotherapy or in any combination regimen in a FRACTION-RCC Sub-Protocol are eligible for treatment on Track 2.
 - (3) Participants who have had prior combination treatment with the same combination agents (or IO agents directed against the same targets) as 1 of the combination regimens in a FRACTION-RCC Sub-Protocol are eligible for study treatment on Track 2 but must be randomized to another combination regimen (as outlined in [Section 5.1.1 Inclusion Criteria](#) of each FRACTION-RCC Sub-Protocol).
 - (4) Participants may have received targeted treatment (see above).
 - (5) After signing informed consent, participants will be required to submit a fresh tumor biopsy prior to treatment as described below [see “6.1.2)j)”]. Eligibility will not be determined by this biopsy.
- f) At the time of screening, participants must have a life expectancy of at least 3 months following their most recent chemotherapy or immunotherapy for entry into all Tracks.
 - i) Participants who wish to be re-randomized to a new study treatment combination in Track 2 following progression on a prior study treatment in Tracks 1 or 2 must have a life expectancy of at least 3 months following the last study treatment.
- g) Participants receiving prior palliative radiotherapy to a non-central nervous system (CNS) lesion must have completed that treatment at least 2 weeks prior to the first dose of study treatment.
 - i) Participants with symptomatic tumor lesions at baseline who may require palliative radiotherapy within 4 weeks of the first dose of study treatment are strongly encouraged to receive palliative radiotherapy prior to enrollment, and they must complete that treatment at least 2 weeks prior to the first dose of study treatment.
- h) Participants must have at least 1 lesion with measurable disease as defined by RECIST v1.1 criteria for solid tumors response assessment (see [Appendix 5](#)).
 - i) Participants with lesions in a previously irradiated field as the sole site of measurable disease will be permitted to enroll, provided that the lesion(s) has demonstrated clear progression and can be measured accurately.
 - i) Participants with toxicity from any prior anti-cancer treatment must have their toxicity returned to Grade ≤ 1 (NCI CTCAE Version 4.03) or baseline before administration of study treatment.
 - i) Participants with Grade ≥ 2 toxicities attributed to prior anti-cancer treatment that are not expected to resolve and result in long-lasting sequelae, such as neuropathy after a platinum-based treatment, are eligible.
 - ii) Grade >1 alopecia or fatigue is permitted.

- j) Participants must allow a tumor biopsy at the following time points: 1) baseline (prior to study treatment); 2) on-study (Day 28 On-treatment); and 3) EOT, defined as at the time of progression or at the time of a clinically significant event (eg, at EOT for participants with PR or SD or at EOT for participants who discontinue treatment due to an AE) provided that the biopsy is at acceptable clinical risk as judged by the investigator for each study treatment regimen to 1) identify predictive biomarkers for both safety and efficacy of a given combination, 2) define the mechanism of action for a particular combination (pharmacodynamic assessment), and 3) determine the mechanisms of resistance to a particular combination.
- i) Participants who do not have accessible or suitable lesions are not eligible.
 - (1) Baseline biopsies may be collected from participants with a single measurable lesion (primary or metastatic), as long as it is not an excisional biopsy.
 - ii) For participants whose pretreatment biopsy yields inadequate tissue quantity or quality (as determined by a pathologist in the central or local laboratory), re-biopsy is permitted.
 - iii) The solid tumor tissue specimen must be a core-needle biopsy or an excisional or incisional biopsy. Fine-needle biopsies, drainage of pleural effusions with cytospins, or punch biopsies are not considered adequate for biomarker review and randomization. Biopsies of bone lesions that do not have a soft tissue component or decalcified bone tumor samples are also not acceptable.
 - iv) The biopsy at progression of disease after treatment on any Track may function as the pretreatment biopsy for subsequent treatment on Track 2.
- k) Study personnel must ensure that the archival tissue block (preferred) or slides samples, if available, are located and shipped to the central laboratory prior to randomization within 6 weeks of signing the written informed consent, as long as this tissue will not be used for the screening biopsy sample.
- l) Participants must have adequate organ function, as defined by the following:
- i) White blood cells $\geq 2,000/\mu\text{L}$ (stable off any growth factor after discontinuation within 2 weeks of the first study treatment administration)
 - ii) Neutrophils $\geq 1,500/\mu\text{L}$ (stable off any growth factor after discontinuation within 2 weeks of the first study treatment administration)
 - iii) Not applicable per Amendment 02
 - iv) Not applicable per Amendment 03
 - v) Alanine aminotransferase (ALT) and aspartate aminotransferase (AST) $\leq 3\times$ institutional upper limit of normal (ULN)
 - vi) Total bilirubin $\leq 1.5\times$ institutional ULN (except for participants with Gilbert's syndrome who must have normal direct bilirubin)

vii) Serum creatinine $\leq 1.5 \times$ institutional ULN or creatinine clearance (CrCl) > 40 mL/min (measured using the Cockcroft-Gault formula below):

$$\text{Female CrCl} = \frac{(140 - \text{age in years}) \times \text{weight in kg} \times 0.85}{72 \times \text{serum creatinine in mg/dL}}$$

$$\text{Male CrCl} = \frac{(140 - \text{age in years}) \times \text{weight in kg} \times 1.00}{72 \times \text{serum creatinine in mg/dL}}$$

- i) Platelets $\geq 100 \times 10^3/\mu\text{L}$ (transfusion to achieve this level is not permitted within 4 weeks of the first study treatment administration)
- ii) Hemoglobin ≥ 9.0 g/dL (transfusion to achieve this level is not permitted within 4 weeks of the first study treatment administration)
- m) Participants must be able to comply with restrictions and prohibited activities/treatments listed in [Section 7.7.1](#).
- n) Participant re-enrollment: This study permits the re-enrollment of a participant who has discontinued the study as a pretreatment failure (eg, participant has not been treated). If re-enrolled, the participant must be re-consented.

3) Age and Reproductive Status

- 4) In addition to the reproductive guidelines noted below, please refer to the individual sub-protocol for additional requirements regarding reproductive guidelines.
 - a) Males and females, ages 18 years or age of majority or older at the time of consent
 - b) Women of child-bearing potential (WOCBP) must have a negative serum or urine pregnancy test (minimum sensitivity 25 IU/L or equivalent units of human chorionic gonadotropin) within 24 hours prior to the start of study treatment. An extension up to 72 hours prior to the start of study treatment is permissible in situations where results cannot be obtained within the standard 24-hour window.
 - c) Women must not be breastfeeding
 - d) WOCBP must agree to follow instructions for method(s) of contraception for the duration of treatment with study treatment(s) plus the time required for the study treatment to undergo approximately 5 half-lives, plus the duration of 1 ovulatory cycle (30 days) for a total of 5 months posttreatment completion (see [Appendix 4](#)). If the half-life of a study treatment in a FRACTION-RCC Sub-Protocol is longer than approximately 5 half-lives of nivolumab, this will be addressed in the FRACTION-RCC Sub-Protocol.
 - e) WOCBP who are continuously not heterosexually active are also exempt from contraceptive requirements and still must undergo pregnancy testing as described in this section.
 - f) Males who are sexually active with WOCBP must agree to follow instructions for method(s) of contraception and fetal protection (see [Appendix 4](#)) for the duration of treatment with study treatment(s) plus approximately 5 half-lives of the study treatment, plus the duration of sperm turnover (90 days), for a total of 7 months posttreatment completion. In addition, male participants must be willing to refrain from sperm donation during this time.
 - g) Azoospermic males are exempt from contraceptive requirements.

Investigators shall counsel WOCBP and male participants who are sexually active with WOCBP on the importance of pregnancy prevention and the implications of an unexpected pregnancy. Investigators shall advise on the use of highly effective methods of contraception ([Appendix 4](#)), which have a failure rate of < 1% when used consistently and correctly.

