The study population consists of participants with advanced (not amenable to curative surgery or radiation treatment) or metastatic (American Joint Committee on Cancer Stage IV) RCC and have histological confirmation of RCC with a clear-cell component. In Track 1, participants must not have received any anti-programmed death 1 (PD-1), anti-programmed cell death ligand 1 (PD-L1), or anti-cytotoxic T lymphocyte antigen 4 (CTLA)-4 treatment prior to this study (participants previously treated with agents other than anti-PD-1, anti-PD-L1, or anti-CTLA-4 are eligible for Track 1). Track 1 participants with favorable risk profile by IMDC Score must have been treated with sunitinib prior to randomization into Track 1 nivolumab plus ipilimumab.

Track 2 participants must have had progressive or recurrent disease during or after anti-PD-1, anti-PD-L1, or anti-CTLA-4 treatment (participants treated with any study treatment targeting PD-1, PD-L1, or CTLA-4 will be considered anti-PD-1, anti-PD-L1, or anti-CTLA-4 treatment experienced, respectively). All participants must allow a tumor biopsy at the following time points: 1) baseline (prior to study treatment); 2) on-study (Day 28 On-treatment); and 3) end of treatment (EOT), defined as at the time of progression or at the time of a clinically significant event (eg, at EOT for participants with partial response (PR) or stable disease or at EOT for participants who discontinue treatment due to an AE) provided that the biopsy is an acceptable clinical risk as judged by the investigator for each study treatment regimen.

Participants must meet the following criteria:

- Must be 18 years of age or older with inoperable, advanced or metastatic RCC
- RCC must be histologically confirmed with a clear cell component.
- Life expectancy of at least 3 months
- Must be evaluated for risk of the disease as defined by International Metastatic RCC Database Consortium (IMDC) score ([Appendix 8](#)).
- If they have received prior palliative radiotherapy to a non-CNS, treatment must be completed 2 weeks prior to first dose.
- Must have at least one measurable lesion (if the only measurable lesion has been irradiated, the lesion must have demonstrated clear progression and be measurable).
- Must agree to 3 biopsies during the study as described in protocol.

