3.2 Background

3.2.1 FRACTION - RCC

Renal cell carcinoma (RCC) accounts for ~3% of all cancers in the US.²² More than 60,000 patients will be diagnosed with RCC in a year, and approximately 13,000 patients will die from advanced disease.²³ Metastatic disease is found in 30% of participants at diagnosis. Close to 90% to 95% of metastatic disease is of the clear-cell histology.²⁴ With the increased use of imaging over the last several decades, the incidence of earlier stage and potentially more curable disease is rising.²³

Multiple scoring systems are available to characterize prognosis in treatment-naïve RCC. Two of the most commonly used are the Memorial Sloan-Kettering Cancer Center (MSKCC) prognostic scoring system and the International Metastatic RCC Database Consortium (IMDC) prognostic scoring system.^{25,26} Each of these systems categorizes patients as favorable, intermediate, or poor risk based on how many adverse prognostic factors are present (0: favorable risk, 1 to 2: intermediate risk, 3 or more: poor risk). The 6 parameters of importance for IMDC prognostic score classification are Karnofsky Performance Status (KPS), time from diagnosis to treatment, hemoglobin value, corrected calcium concentration, absolute neutrophil count, and platelet count.

The 5 parameters included in the MSKCC prognostic score are KPS, nephrectomy status, hemoglobin value, lactate dehydrogenase, and corrected calcium concentration. Time from diagnosis to treatment is often used in place of nephrectomy status. With each system, total number of adverse prognostic factors present has been shown to correlate with OS. Approximately 25% of patients are in the favorable-risk group, 50% are in the intermediate-risk group, and 25% are in the poor-risk group (OS: ~9 months). In an analysis of 1,028 patients scored using the IMDC system, median OS for favorable-, intermediate-, and poor-risk patients is 43.2 months, 22.5 months, and 7.8 months, respectively.²⁷

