Each participant who is randomized will be assigned a unique randomization number. This is not the primary identifier for the participant but used for the randomization schedule. The primary identifier will be the PID described above, for use on the case report form (CRF) and source documents. A participant being re-randomized in Track 2 will be assigned a different randomization number but will retain the same PID. Randomization numbers will be assigned using a Central Randomization System in the order in which participants qualify for study treatment, not in the order of study enrollment. Randomization ratios within each Track will be specified in each FRACTION-RCC Sub-Protocol. If, within a given Track, study treatment arms from more than 1 FRACTION-RCC Sub-Protocol within the FRACTION-RCC Master Protocol are simultaneously open to enrollment, then a new participant could be assigned to any of the open study treatment arms. In Track 1, randomization of participants will be stratified by whether or not the participant has had prior TKI treatment. In Track 1, participants will be randomized to newly added study treatment arms/study treatments (through FRACTION-RCC Sub-Protocols) in a ratio as specified in each new FRACTION-RCC Sub-Protocol. New randomization schedules for new FRACTION-RCC Sub-Protocols will be generated. If accrual for current FRACTION-RCC Sub-Protocols is still ongoing, participants will be allocated to the existing randomization schedule or new randomization schedule based on a prespecified allocation ratio. Details of allocation ratio will be specified in the new FRACTION-RCC Sub-Protocol. In Track 2, participants will be randomized to existing study treatment arm/study treatments and newly added study arm/study treatments with equal probability.

Prespecified study treatment arm caps (according to Simon 2-stage [optimal] design) will be utilized to control the accrual for each combination study treatment arm under different Tracks (Tracks 1 and 2). The cap for the nivolumab in combination with ipilimumab control arm under Track 1 will be set equal to the largest cap among its corresponding experimental arms. In the event that 1 or more participants go off study without being evaluable for response (ie, with no postbaseline tumor measurements and no evidence of clinical progression or death due to disease

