Abbreviations: DOR = duration of response; ORR = overall response rate; OS = overall survival; PFSR = progression free survival rate.

Track 1 - Anti-PD-1, Anti-PD-L1, and Anti-CTLA-4 Treatment-naïve Participants

The following additional analyses will be performed for Track 1 anti-PD-1, anti-PD-L1, and anti-CTLA-4 treatment-naïve participants at the end of Stage 2. These efficacy analyses will be performed when the study treatment arms have been fully enrolled and followed up for at least 6 months. A descriptive odds ratio and estimate of the difference in ORRs, along with corresponding 2-sided 95% CIs, will be provided to evaluate differences between the 2 randomized study treatment arms (FRACTION- RCC study treatment combination arm and nivolumab in combination with ipilimumab control arm). Additionally, for each study treatment arm, the ORR and corresponding 95% CIs will be calculated using Clopper-Pearson method. A descriptive hazard ratio and corresponding 2-sided 95% CI of PFS and OS will be estimated in a Cox proportional hazards model using study treatment as a single covariate to evaluate difference between the 2 study treatment arms (experimental and control arms). The PFS and OS curves for each study treatment arm will be estimated. Two-sided 95% CIs for median PFS and OS will be computed. PFSR at 24 weeks and survival rates at certain time points (eg, 2 years) will be estimated. Associated 2-sided 95% CIs will be calculated.

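### Track 1: the prior-sunitinib rule is worded for the control arm only; if it is meant that way, the experimental-versus-control comparison includes participants who could not have been randomized to control

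*Combined protocol and SAP*

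**What the plan says.** Criterion 2)e)i)(6) in Section 6.1 reads "participants with favorable risk profile by IMDC Score must have been treated with sunitinib prior to randomization into Track 1 nivolumab plus ipilimumab". The Study Population part of the Synopsis carries the same arm-specific wording: "Track 1 participants with favorable risk profile by IMDC Score must have been treated with sunitinib prior to randomization into Track 1 nivolumab plus ipilimumab". The other current Track 1 criteria name no arm.

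Section 6 introduces all of these as conditions of study entry: "For entry into the FRACTION-RCC study (per FRACTION-RCC Master Protocol), the following criteria MUST be met prior to dosing on Day 1". It allows no exceptions. On assignment, Section 7.2 says that when arms from several Sub-Protocols are open, "then a new participant could be assigned to any of the open study treatment arms". It describes no restricted randomization for any Track 1 subgroup. On balance between arms it says "In Track 1, randomization of participants will be stratified by whether or not the participant has had prior TKI treatment". IMDC risk group is not a stratification factor.

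For Track 1 at the end of Stage 2, Section 10.3.1 plans a descriptive odds ratio and ORR difference "to evaluate differences between the 2 randomized study treatment arms". It also plans hazard ratios for PFS and OS from a Cox model with treatment as the only covariate. It does not limit these estimates to participants who could have received either arm.

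**The concern.** Taken literally, criterion (6) lets a favorable-risk, sunitinib-naive participant enter Track 1 but closes the control arm to that person. The control arm then has fewer favorable-risk participants than the experimental arm by construction, not by chance. Section 3.2.1 shows how strongly risk group predicts survival: median OS is 43.2, 22.5 and 7.8 months for favorable, intermediate and poor risk. It also puts the group at issue at a quarter of patients: "Approximately 25% of patients are in the favorable-risk group".

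Stratifying by prior TKI does not repair this. Prior TKI is not the same as prior sunitinib, since Section 3.2.1 lists other TKIs. Under the literal reading, the TKI-naive stratum of the control arm would contain no favorable-risk participants at all, while the same stratum of the experimental arm would. The planned Cox model also leaves the stratum out.

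At stake are the between-arm estimates. The primary objective (Table 4-1) is framed relative to the control where applicable. Sections 10.1 and 10.1.1 also have the sponsor weigh the relative performance of arms before continuing or stopping one.

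**Working it through.** **The plan's own Track 1 figures.** The documents give no power or precision for the experimental-versus-control comparison. The nearest stated figures are the single-arm Simon characteristics in Section 10.1.1 (continue if more than 8/24, efficacy if more than 24/63). Exact binomial calculation gives:
- probability of stopping at Stage 1 when the true ORR is 30%: 0.725 (stated 73%)
- false positive rate: 0.0497 (stated 5%)
- power at 35/40/45/50%: 0.206/0.478/0.743/0.903 (stated 20/48/74/90%)
- expected n under 30%: 24 + (1 − 0.725) × 39 = 34.7 (stated 34.5, which is what the rounded 0.73 gives)

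These agree to rounding. The rule does not use the control arm.

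**Inputs for the case-mix check.** From Section 3.2.1: risk mix 25/50/25% and median OS 43.2/22.5/7.8 months. Assumed: exponential survival within each risk group, no treatment effect, follow-up ending at 24 months, and a trial case mix equal to the cited one. The share *f* of favorable-risk participants who are sunitinib-naive is not in the documents, so it runs from 25% to 100%.

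**Step 1: survival at 24 months by risk group.** S(24) = 2^(−24/median), giving 0.680, 0.477 and 0.119.

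**Step 2: favorable-risk share by arm.**
- Control: 0.25(1 − f) / (1 − 0.25f).
- Experimental, scenario A: stays at 25%.
- Experimental, scenario B (all barred participants go to one experimental arm, everyone else is split 1:1): [0.125(1 − f) + 0.25f] / [0.5(1 − 0.25f) + 0.25f].

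Intermediate and poor risk fill the remainder in the ratio 2:1. At f = 1 the control mix is 0/66.7/33.3% and the scenario B experimental mix is 40/40/20%.

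**Step 3: 2-year OS.** At f = 1:
- control: 0.667 × 0.477 + 0.333 × 0.119 = 0.358
- experimental, A: 0.25 × 0.680 + 0.50 × 0.477 + 0.25 × 0.119 = 0.438
- experimental, B: 0.40 × 0.680 + 0.40 × 0.477 + 0.20 × 0.119 = 0.487

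**Step 4: unadjusted Cox hazard ratio.** With arm densities f_E, f_C and survival S_E, S_C as mixtures of the three exponentials, solve for h in ∫₀²⁴ [f_E(1 − p) − f_C p] dt = 0, where p = hS_E / (hS_E + S_C). This weights the arms equally. Weighting by the unequal arm sizes that scenario B produces leaves the result unchanged to three decimals.

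| f | Control favorable | A: HR | B: experimental favorable | B: HR |
|---|---|---|---|---|
| 25% | 20% | 0.96 | 29% | 0.92 |
| 50% | 14% | 0.91 | 33% | 0.85 |
| 75% | 8% | 0.86 | 37% | 0.77 |
| 100% | 0% | 0.81 | 40% | 0.70 |

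If the barred participants are spread over two or three experimental arms, the scenario B range becomes about 0.94 to 0.75 or 0.94 to 0.77.

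**Step 5: dilution.** The rule entered with Revised Protocol 05. If half of accrual came earlier (an assumption; the split is not given), the barred group at f = 100% is half as large. Scenario B then gives the 50% row: 0.85 instead of 0.70.

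**Step 6: ORR.** The false difference is (favorable ORR − other ORR) × (difference in favorable share). For an assumed gap of 10 to 20 points in either direction under scenario A, it runs from 0.10 × 0.05 = 0.5 points to 0.20 × 0.25 = 5 points. The documents do not give the sign.

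**Step 7: under a Track-wide rule** the expected mix is the same in both arms and the no-effect hazard ratio is 1.00.

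**The case against.** The strongest reply is that the rule may cover all of Track 1. It sits among study-entry criteria that must all be met. Section 9 has eligibility confirmed before randomization, Section 7.2 treats only fully eligible participants as ready to be randomized, and any open arm may follow. Where the protocol does want arm-restricted assignment, in Track 2 criterion (3), it says so and points to the Sub-Protocols. No passage expressly admits favorable-risk, sunitinib-naive participants to an experimental arm. The Sub-Protocols, which could settle the point, are not among the documents. This stands. A reader might infer that the Track 1 comparison is confounded by prognosis as a matter of fact; the documents show only that it would be under the literal reading. The Track-wide reading has its own difficulty: it leaves the words naming the combination with no function.

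The reply also limits the size and reach of the problem. The figures concern OS, which is exploratory, in a comparison labelled descriptive, and the numerical go/no-go guideline is single-arm. The cited risk mix may not carry over to a trial that requires KPS of at least 70% in Track 1 and admits TKI-pretreated participants. A reader might also infer that the PFS hazard ratio and ORR difference favor the experimental arm. The documents give no ORR or PFS by risk group under these treatments, so that does not follow.

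The descriptive label does not answer everything: an estimate that is off by design still informs the sponsor's review of relative performance. Asking for a change to the randomization system would be pointless, since one participant remains, in safety follow-up.

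**Conclusion.** The point holds as a conditional one. Section 6.1 and the Synopsis tie the sunitinib requirement to one arm, Sections 6 and 7.2 read as if no arm-specific bar exists, and the two must be reconciled. If the rule is arm-specific, the planned unadjusted comparison departs from no effect in the experimental arm's favor for OS. The hazard ratio is 0.96 to 0.81 in the milder scenario and 0.92 to 0.70 in the more severe one, and closer to 1 to the extent that accrual preceded Revised Protocol 05. Those ranges rest on the assumed sunitinib-naive share, exponential survival by risk group, the cited 25/50/25% mix and 1:1 allocation of participants eligible for both arms. ORR and PFS may be shifted, in a direction the documents do not establish. The single-arm Simon rule makes no use of the control comparison.

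**What to change.** State in Section 6.1 and the Synopsis whether criterion (6) applies to all of Track 1 or only to the nivolumab plus ipilimumab arm, and make Section 7.2 agree. Which scope is clinically right is for the sponsor.

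In Section 10.3.1 and the SAP, before database lock, limit the Track 1 experimental-versus-control odds ratio, ORR difference and hazard ratios to participants who were eligible for both arms when randomized, under the protocol version then in force. Describe favorable-risk, sunitinib-naive participants who fall outside that set separately, and keep them in the single-arm Simon evaluation. If the rule is Track-wide, the restriction removes no one randomized under it.

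The cost is wording plus an analysis flag. Table 2-1 already collects IMDC score and prior systemic therapy, and Section 10.3 has the SAP finalized before database lock. The comparison loses a few experimental-arm participants. IMDC scores may be missing for participants randomized before the revision, because Table 2-1 promises retrospective collection only where possible; the SAP should say how those cases are handled.
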